POM_{WP} Pain On Movement of worst procedure (leading to maximum pain at

baseline)

POM_{WP}AUC₇₂ Area under the curve of POM_{WP} assessed until Day 4 morning, i.e. 72

hours after start of treatment

POM_{WP}AUC₁₂₀ Area under the curve of POM_{WP} assessed until Day 6 morning, i.e. 120

hours after start of treatment

BI Trial No.: 1358.1

c03317678-02 Trial Protocol Page 12 of 69

Proprietary confidential information © 2016 Boehringer Ingelheim International GmbH or one or more of its affiliated companies

RDC Remote Data Capture

REML Restricted Maximum Likelihood

REP Residual Effect Period, after the last dose of medication with measureable

drug levels or pharmacodynamic effects still likely to be present

SAE Serious Adverse Event SBP Systolic Blood Pressure

SmPC Summary of Product Characteristics SOP Standard Operating Procedure

SUSAR Suspected Unsuspected Serious Adverse Events

TCM Trial Clinical Monitor

TENS Transcutaneous Electrical Nerve Stimulation

TRPV1 Transient Receptor Potential Vanilloid 1

TS Treated Set

TSAP Trial Statistical Analysis Plan

ULN Upper Limit of Normal VAS Visual Analogue Scale VRS Visual Response Scale

Trial Protocol

c03317678-02 Page 13 of 69

Proprietary confidential information © 2016 Boehringer Ingelheim International GmbH or one or more of its affiliated companies

1. INTRODUCTION

1.1 MEDICAL BACKGROUND

Back pain is a very common disorder with a point prevalence of approximately 35% in Germany [P11-08387]. In most cases specific causes cannot be identified (i.e. "unspecific low back pain"). Usually, low back pain is a self-limiting disorder, and approximately 90% of patients experience remission within 6 weeks. Musculoskeletal pain in the back area is worsened through a vicious circle of excessive muscle (force) load inducing pain (by minor muscle injury and local muscle ischaemia) that causes non-physiological posture, which in turn causes further pain.

Neck pain is becoming increasingly common throughout the world. The point prevalence of neck pain ranges from 0.4% to 41.5% (mean: 14.4%); and 1 year prevalence ranges from 4.8% to 79.5% (mean: 25.8%). Prevalence is generally higher in women, higher in highincome countries compared with low- and middle-income countries and higher in urban areas compared with rural areas [R12-4817]. Much neck pain is not attributable to a specific disease or disorder and is labelled as "soft-tissue" rheumatism or muscular/ mechanical/ postural neck pain [R15-2389].

Acute back/ neck pain is often treated with over the counter (OTC) analgesics, such as paracetamol, ibuprofen, or naproxen. Other treatment options are local heat [P11-08754] and hyperaemisation inducing agents [R11-2672]. Local heat and hyperaemisation inducing treatment were shown to augment blood flow and haemoglobin oxygenation in the skin and in the muscles [R11-2636, P11-05079]. Thus, such treatments can be assumed to be beneficial in the treatment of such musculoskeletal conditions.

Remedies against acute back/ neck pain, especially in an OTC environment, are required to reduce back discomfort fast and effectively while being tolerated well.

NSAIDs have been used since decades for the treatment of back and neck pain. A systematic review concluded that NSAIDs are effective for short-term symptomatic relief in patients with acute and chronic low back pain without sciatica. However, effect sizes are small [P08-09510]. In a recent review [P15-04711] topical options for the treatment of back/neck pain has been discussed. In a clinical trial a hyperaemisation inducing agent has been shown to reduce back/neck pain with low incidence of side effects [P11-00252].

Topically applied remedies seem to have a low potential for systemic side effects and interactions with other (including systemic) medications.

Page 14 of 69

Proprietary confidential information © 2016 Boehringer Ingelheim International GmbH or one or more of its affiliated companies

1.2 **DRUG PROFILE**

Diclofenac

c03317678-02

Diclofenac is a non-steroidal drug with anti-inflammatory and analgesic activity. It inhibits the enzyme cyclooxygenase, and so directly inhibits the biosynthesis of prostaglandins and thromboxanes from arachidonic acid.

The topical usage of diclofenac in acute pain conditions is considered well established and is associated with an improved safety profile due the low systemic plasma concentrations [P13-15601, P08-12601].

Capsaicin

Capsaicin is a highly selective and potent exogenous agonist for the transient receptor potential vanilloid 1 (TRPV1) receptor. When activated TRPV1 opens transiently and initiates a depolarization mediated by influx of sodium and calcium ions. In the nociceptive (mostly C- and some Aδ-fibers) nerve endings which selectively express TRPV1, capsaicinmediated depolarization results in action potentials, which are transmitted to the spinal cord and brain and usually reported as warming, burning, stinging or itching sensations.

Capsaicin causes an initial excitation of the neurons and a short period of hypersensitivity. This is followed by a refractory period with reduced sensitivity and, after repeated applications, persistent desensitization and decreased sensitivity to pain. There is also evidence that capsaicin treatment may interfere with substance P synthesis [P13-09858].

Combination rationale

Capsaicin has been shown to act as a penetration enhancer (e.g. for indomethacin [R10-0978], naproxen [R14-1637] and thus, might improve the penetration rate and absorption of diclofenac. In addition, both substances have different pharmacodynamics properties and complementary mechanisms of action.

By combining both actives in a topical formulation, the new combination product will lead to an increased pain relief compared to the respective mono products.

For a more detailed description of the drug profile refer to the current Investigator's Brochure (IB, [c03404356]) which is included in the Investigator Site File (ISF).

Proprietary confidential information © 2016 Boehringer Ingelheim International GmbH or one or more of its affiliated companies

2. RATIONALE, OBJECTIVES, AND BENEFIT - RISK ASSESSMENT

2.1 RATIONALE FOR PERFORMING THE TRIAL

Diclofenac and capsaicin ointments/gels have been used for decades to treat complaints of the musculoskeletal system. However, no clinical trials have been performed to demonstrate analgesic effects for the combination of diclofenac and capsaicin in treatment of back or neck pain.

The aim of this study is to assess the efficacy and tolerability of diclofenac/capsaicin gel in comparison to diclofenac, capsaicin, and placebo gels for the treatment of acute back or neck pain to obtain market authorizations for this indication.

2.2 TRIAL OBJECTIVES

The objective of this pivotal study is to assess the efficacy and tolerability of a topical formulation gel of the combination of diclofenac and capsaicin in comparison to gels with diclofenac alone, capsaicin alone, and placebo for the treatment of acute back pain or neck pain.

The primary objective of this trial is to demonstrate superior efficacy of a formulation containing a combination of 2% diclofenac and 0.075% capsaicin over placebo and over formulations containing 2% diclofenac alone and 0.075% capsaicin alone for the treatment of acute back or neck pain.

A secondary objective is to assess the safety and tolerability of the combination of diclofenac and capsaicin in comparison to gels with diclofenac alone, capsaicin alone.

2.3 BENEFIT - RISK ASSESSMENT

Topical application forms containing either diclofenac or capsaicin have been in clinical use for a long time and the available safety and tolerability data show that both are well tolerated and safe. Data from post marketing surveillance show that most of the reported unwanted effects of capsaicin gels are in line with the mechanism of action, e.g. skin burning sensation, erythema and pruritus for capsaicin gels. The most common side effects of diclofenac are application site reactions, including erythema, itching, burning sensation and rash. A combination of both safety profiles is expected for the combination of diclofenac and capsaicin.

Overall, the long term clinical experience with diclofenac or capsaicin gels and the aforementioned safety profiles of both present a favourable benefit risk assessment which would support proceeding with this trial.

Although very rare in topical administration, a potential for drug-induced liver injury is under constant surveillance by sponsors and regulators. Therefore, this trial requires timely

c03317678-02 Trial Protocol

Page 16 of 69

Proprietary confidential information © 2016 Boehringer Ingelheim International GmbH or one or more of its affiliated companies

detection, evaluation, and follow-up of laboratory alterations in selected liver laboratory parameters to ensure patients' safety, see also Section 5.3.6.1.

Proprietary confidential information © 2016 Boehringer Ingelheim International GmbH or one or more of its affiliated companies

3. DESCRIPTION OF DESIGN AND TRIAL POPULATION

3.1 OVERALL TRIAL DESIGN AND PLAN

This trial is a prospective, randomised, double-blind, parallel group, multi-centre trial to show superiority in terms of reduction of Pain on Movement (POM) of a topical combination containing diclofenac 2% and capsaicin 0.075% compared to placebo, as well as to diclofenac 2% and capsaicin 0.075% when applied twice daily over 4 to 7 days to patients with acute back pain or neck pain. A total of approximately 800 patients will be randomised to the treatment groups diclofenac + capsaicin, diclofenac, capsaicin and placebo in a 3:3:3:1 ratio in order to achieve 700 patients eligible for the assessment of the primary endpoint.

After a screening evaluation (Visit 1), eligible patients will be randomised into the double-blind treatment phase of the trial. After administration of the first treatment, the patients will administer the second application of the trial medication in the evening at home. They will return to the trial site for four more visits (Visits 2 to 5) in the morning and in the evening of the following day (Day 2) and in the morning of Days 3 and 4 and thereby be dosed while at the site. Evening applications on Day 3 and Day 4 will be administered by the patients at home. Thereafter, the treatment will be administered at home for one more day (Day 5). The patients will then return to the trial site for final assessments (Visit 6) in the morning of Day 6. The trial participation will be concluded by a telephone call (Visit 7T) for follow-up on adverse events (AEs) on Day 8.

Depending on the severity of a patient's condition and on a patient's availability, the treatment-period at home (Day 5) could be skipped or extended by one or two days. Visit 6 should then be performed on the day immediately following to that shortened or extended period.

The interval between two applications of the trial medication should be 12 hours. This interval could be shortened or extended by 4 hours as long as no more and no less than two applications are administered on each treatment day.

Patients who discontinue the application of the trial medication prematurely, should be encouraged to contact the site immediately so that Visits 6 and 7T could be performed on the day immediately after discontinuation.

The study will be conducted at approximately 20 study centres in Germany and Russia. The trial will end with completion of the last follow-up call (Visit 7T) with the last patient. For a graphical representation of the trial, see Figure 3.1: 1.

c03317678-02

Page 18 of 69

Proprietary confidential information © 2016 Boehringer Ingelheim International GmbH or one or more of its affiliated companies

[figure not shown]

Figure 3.1: 1 Trial design, R = randomisation

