- B M = Morning; E = Evening; Morning visits should generally be performed between 7:00 am and 11:00 am.
- C Visits 2 and 3 need to be planned so that the evening application of the trial medication can be administered 12 hours (±4 hours) after the morning application.
- Date of Visit 6 has to be agreed based on patient's availability and severity of pain. Standard treatment duration is 5 days (Day 1-5) with Visit 6 on Day 6. Treatment could be shortened to 4 days (with Visit 6 on Day 5) or extended to 6 days (with Visit 6 on Day 7; home procedures indicated in the Flow Chart for Day 5 to be repeated on Day 6) or 7 days (with Visit 6 on Day 8; home procedures indicated in the Flow Chart for Day 5 to be repeated on Day 6 and 7). Visit 7T should be performed at least 2 days and no later than 4 days after Visit 6.
- E For women of childbearing potential only

c03317678-02 Trial Protocol Page 7 of 69

Proprietary confidential information © 2016 Boehringer Ingelheim International GmbH or one or more of its affiliated companies

- G Parameters to be assessed by the patient 0.5 (±5 min), 1 (±10 min but before POM assessments), 3 (±15 min) and 6 (±15 min) hours after the morning application of the trial drug. Results will be entered into the patient diary.
- H Pre = before application; Apl = Application; Post = after application. The application time at each visit is to be documented in the eCRF.
- I Assessment 1 hour (± 10 min) after application of trial medication
- J Optional second dispense of rescue medication
- K Hm = Home procedure; Fllw up = Follow up
- L All five POM assessments need to be performed at Visit 1 before application. Once POM_{WP} is determined, only POM_{WP} and the other POM procedures related to the same stratum (either back or neck pain) as POM_{WP} need to be performed at subsequent assessments (see Section 5.2.1)
- M To be assessed by the patient at home directly before and 1 hour (±10 min) after the morning application of the trial drug
- N To be assessed 1 hour (±10 min) after application of the trial drug and before POM assessments

BI Trial No.: 1358.1

c03317678-02 Trial Protocol Page 8 of 69

Proprietary confidential information © 2016 Boehringer Ingelheim International GmbH or one or more of its affiliated companies

TABLE OF CONTENTS

TITLE I	PAGE	1
CLINIC	AL TRIAL PROTOCOL SYNOPSIS	2
FLOW (CHART	5
TABLE	OF CONTENTS	8
ABBRE	VIATIONS	11
1.	INTRODUCTION	13
1.1	MEDICAL BACKGROUND	13
1.2	DRUG PROFILE	14

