3.3.4 Removal of patients from therapy or assessments

3.3.4.1 Removal of individual patients

An individual patient is to be withdrawn from trial treatment if:

- The patient withdraws consent for study treatment or study participation, without the need to justify the decision.
- The patient needs to take concomitant drugs that interfere with the investigational product (see Section 3.3.3) or other trial medication. See Section 4.2.2 for further details.
- The patient can no longer be treated with trial medication or rescue medication for other medical reasons (such as surgery, adverse events, other diseases, or pregnancy)

If a patient becomes pregnant during the trial the study medication will be stopped, the patient will be discontinued from the trial and the patient will be followed up until birth or otherwise termination of the pregnancy.

Trial Protocol

c03317678-02 Page 23 of 69

Proprietary confidential information © 2016 Boehringer Ingelheim International GmbH or one or more of its affiliated companies

A patient can be discontinued after discussion between Sponsor and Investigator if eligibility criteria are being violated, or if the patient fails to comply with the protocol (e.g. nonattendance at study assessments).

Patients who drop out during the screening prior to randomisation will be considered screening failures. They will be recorded as screening failures in the eCRF and no further follow-up is required. The data will be included in the trial database and will be reported.

Patients who discontinue or withdraw from the study after randomisation will be considered as "early discontinuations" and the reason for this premature discontinuation must be recorded in the eCRF. The Investigator must inform the sponsor within 24 hours via IRT (see Section 4.1) about any premature discontinuation of a subject. The data will be included in the trial database and will be reported. Given the patient's agreement, the patient will undergo the procedures for early treatment discontinuation and follow up (Visits 6 and 7T) as outlined in the Flow Chart and Section 6.2.3.

For all patients the reason for withdrawal (e.g. adverse events) must be recorded in the eCRF. These data will be included in the trial database and reported.

Discontinuation of the trial by the sponsor 3.3.4.2

Boehringer Ingelheim reserves the right to discontinue the trial overall or at a particular trial site at any time for the following reasons:

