5.3.7 Adverse event collection and reporting

AE Collection

The Investigator shall maintain and keep detailed records of all AEs in their patient files. The following must be collected and documented on the appropriate eCRF by the Investigator (see also Figure 5.3.7: 1):

From signing the informed consent onwards through the Residual Effect period (REP), all AEs (serious and non-serious), and AESIs must be reported. However, if an individual patient discontinues trial medication prematurely but stays in the trial (i.e. if further visits including

Trial Protocol Page 42 of 69

Proprietary confidential information © 2016 Boehringer Ingelheim International GmbH or one or more of its affiliated companies

telephone visits, or vital status assessments are planned) from then on and until the individual patient's end of the trial the Investigator must report related SAEs and related AESIs.

[figure not shown]

Figure 5.3.7: 1 Graphical depiction of the requirements for AE collection

The REP is defined as 48 hours after the last trial medication application. All AEs which occurred through the treatment phase and throughout the REP will be considered as on treatment please see Section 7.3.4. Events which occurred after the REP will be considered as post treatment events.

After the last per protocol contact the Investigator does not need to actively monitor patients for AEs. However, if the Investigator becomes aware of SAEs or AESIs that occurred after the last per protocol contact, the SAEs and AESIs should be reported by the Investigator to the Sponsor if considered relevant by the Investigator.

AE reporting to sponsor and timelines

The Investigator must report SAEs, AESIs, and non-serious AEs which are relevant for the reported SAE or AESI, on the BI SAE form via fax immediately (within 24 hours) to the Sponsor's unique entry point (country specific contact details will be provided in the ISF). The same timeline applies if follow-up information becomes available. In specific occasions the Investigator could inform the Sponsor upfront via telephone. This does not replace the requirement to complete and fax the BI SAE form.

With receipt of any further information to these events, a follow-up SAE form has to be provided. For follow-up information the same rules and timeline apply as for initial information.

Information required

For each AE, the Investigator should provide the information requested on the appropriate

Trial Protocol

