6. INVESTIGATIONAL PLAN

6.1 VISIT SCHEDULE

This trial consists of 6 clinical visits. For the follow-up contact (Visit 7T) the investigator will contact the patient by phone.

If a Visit 2-5 is missed, it should not be re-scheduled. However subsequent visits should follow the original visit schedule. If Visit 6 or Visit 7T is missed, this visit should be rescheduled to the closest opportunity.

All trial visits except for Visit 3 should take place in the morning, i.e. ideally be started and completed between 7:00 a.m. and 11:00 a.m. Patients must adhere to the visit schedule as specified in the Flow Chart. Visits 2 (Day 2 morning) and 3 (Day 2 evening) need to be scheduled such that the trial medication could be applied according to the required dosing interval of 12 hours (± 4 hours).

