6.2.3 Follow Up Period and Trial Completion

All study procedures according to the Flow Chart should be performed.

Patients who want to discontinue the trial treatment prematurely should be asked to have Visit 6 in the morning after the last application of the trial medication and to have a Visit 7T at least 48 hours after that last application.

Patients who at the end of their trial participation still require treatment for the trial indication should be treated according to local standard of care.

Proprietary confidential information © 2016 Boehringer Ingelheim International GmbH or one or more of its affiliated companies

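### Protocol Section 3.1 allows Visit 7T on the day after early discontinuation, against Section 6.2.3 (at least 48 h after the last application) and Flow Chart footnote D (2 to 4 days after Visit 6)

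*Protocol*

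**What the plan says.** Four places in the protocol bear on the timing of Visit 7T after an early stop.

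- **Section 3.1** (design overview): such patients should be "encouraged to contact the site immediately so that Visits 6 and 7T could be performed on the day immediately after discontinuation".
- **Section 6.2.3**: these patients should have Visit 6 on the morning after the last application and are asked "to have a Visit 7T at least 48 hours after that last application".
- **Flow Chart footnote D**: "Visit 7T should be performed at least 2 days and no later than 4 days after Visit 6".
- **Section 3.3.4.1**: with the patient's agreement, early discontinuations undergo "the procedures for early treatment discontinuation and follow up (Visits 6 and 7T) as outlined in the Flow Chart and Section 6.2.3".

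Section 6.1 adds: "Patients must adhere to the visit schedule as specified in the Flow Chart".

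The call's purpose is given in Section 3.1: "The trial participation will be concluded by a telephone call (Visit 7T) for follow-up on adverse events (AEs) on Day 8". On adverse events, Section 5.3.7 says: "From signing the informed consent onwards through the Residual Effect period (REP), all AEs (serious and non-serious), and AESIs must be reported". It sets the residual effect period (REP) at 48 h from the last application and lifts the duty of active monitoring once the last per-protocol contact has taken place. Protocol Section 7.3.4 counts events up to the end of the REP as treatment-emergent. SAP Table 6.1: 2 likewise defines on-treatment as running to the last application plus 2 days.

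**The concern.** Three current provisions time the same telephone call for the same patients, and one does not fit the other two. Visit 7T is the last planned contact and exists to collect adverse events. If it takes place the day after the last application, active follow-up stops inside the window that the safety tables treat as on-treatment. New events that start later in that window and that the patient does not volunteer could go unrecorded. Those affected would be the early stoppers, some of whom may have stopped because of tolerability. Safety and tolerability are the trial's secondary objective (Section 2.2).

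**Working it through.** The plan gives no figure to reproduce here. The check is a comparison of timing rules, followed by clock arithmetic.

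**Rules side by side**

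| Source | Visit 6 | Visit 7T |
|---|---|---|
| Section 3.1 | day after discontinuation | same day as Visit 6 |
| Section 6.2.3 | morning after last application | at least 48 h after last application |
| Footnote D | (sets Visit 6 by treatment length) | 2 to 4 days after Visit 6 |

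*Against footnote D.* Two visits on one day are 0 days apart, and the minimum is 2. This holds however discontinuation is dated.

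*Against Section 6.2.3.* This depends on what discontinuation means. Let the last application be on day d at clock hour a, and the call on day d + k at clock hour c. Then

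elapsed = 24k − a + c, and uncovered REP = max(0, 48 − elapsed).

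If discontinuation is dated to day d, then k = 1. Since a is above 0 and c is at most 24, elapsed is always below 48 h, so the 48 h rule fails at any clock times. If it is dated one day later, k = 2; two days later, k = 3.

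**Inputs.** The 48 h REP comes from Section 5.3.7. The 07:00–11:00 window comes from footnote B and Section 6.1 and applies to morning visits. Dose times are assumed. The time of the call is assumed too: the current Flow Chart gives no time of day for Visit 7T, whereas Section 6.1 puts every visit except Visit 3 in the morning. Two sets are therefore used: narrow (dose 07:00–19:00, call 07:00–11:00) and wide (dose 07:00–23:00, call 07:00–24:00).

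| Discontinuation dated to | Clock times | Least uncovered | Most uncovered |
|---|---|---|---|
| day d (k = 1) | narrow | 48 − (24 − 7 + 11) = 20 h | 48 − (24 − 19 + 7) = 36 h |
| day d (k = 1) | wide | 48 − (24 − 7 + 24) = 7 h | 48 − (24 − 23 + 7) = 40 h |
| day d + 1 (k = 2) | narrow | 0 h (dose 07:00, call 07:00: 48 − 7 + 7 = 48 h elapsed) | 48 − (48 − 19 + 7) = 12 h |
| day d + 1 (k = 2) | wide | 0 h | 48 − (48 − 23 + 7) = 16 h |
| day d + 2 (k = 3) | wide | 0 h | 0 h (shortest elapsed 72 − 23 + 7 = 56 h) |

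**Under the correct rule.** With Visit 6 at 07:00 on d + 1 and the call 48 h after it, elapsed time is (24 − 23 + 7) + 48 = 56 h after a 23:00 dose and (24 − 7 + 7) + 48 = 72 h after a 07:00 dose. No part of the REP is uncovered.

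**Which events could be missed.** Section 5.3.7 continues: "However, if an individual patient discontinues trial medication prematurely but stays in the trial", and from that point it asks only for related SAEs and related AESIs. If full reporting through the REP still applies to these patients, any new adverse event in the uncovered hours is at stake. If the narrower duty starts at discontinuation, only related SAEs and related AESIs are, and moving the call would not recover non-serious events. The text does not settle which reading applies.

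**The case against.** The strongest reply is that the protocol already handles this. The section on withdrawal (3.3.4.1) points to the Flow Chart and Section 6.2.3, not to Section 3.1, and Section 6.1 makes the Flow Chart schedule binding. The Section 3.1 sentence is permissive and mainly urges prompt contact. Reporting through the REP does not depend on when the call is made, and known events must be followed until resolved or sufficiently characterised, even after trial completion. The only listed AESI, hepatic injury, is defined by laboratory values, and the scheduled safety laboratory tests are at Visits 1 and 6, not at the call. The safety analyses are descriptive.

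Most of this stands, and it is why the point is minor. Two further parts of the reply also stand. Section 3.1's Day 6 and Day 8 schedule describes patients on standard treatment, so it is not itself a rule that early stoppers break; it only shows the intended two-day spacing. And the 07:00–11:00 window for the call is contestable, so the wide range is the safer one to cite.

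What does not stand is that the sentence is therefore consistent. It is a stated rule for early stoppers and names both visits and one day. A correct cross-reference elsewhere does not change what it says.

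**Conclusion.** The inconsistency is real and minor. The conflict with footnote D holds under every reading that puts both visits on that one day. The conflict with Section 6.2.3 holds whenever discontinuation is dated to the day of the last application, and for some clock times when it is dated one day later.

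For a site that followed Section 3.1, the uncovered part of the 48 h REP is 7 to 40 h in the first case (20 to 36 h on the narrow times), 0 to 16 h in the second (0 to 12 h), and 0 h if discontinuation is dated two days later. These hours rest on assumed dose and call times and illustrate the gap; they do not measure lost data. What could be lost is limited to new-onset events that the patient does not report unprompted. No number of patients or events can be derived. The primary and secondary efficacy analyses, alpha, power and analysis sets do not depend on Visit 7T.

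**What to change.** Reword the Section 3.1 sentence so that only Visit 6 falls on the day after discontinuation. Add that Visit 7T follows no sooner than 48 h after the last application and 2 to 4 days after Visit 6, in line with Section 6.2.3 and footnote D. The cost is one sentence: the call is already planned, and no visit, procedure, analysis or other section changes.

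This edit does not decide which adverse events are reportable after an early stop. That depends on the sentence in Section 5.3.7 about patients who stop medication but stay in the trial, which would need its own clarification.
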